4.12. Biomarker Variable(s)

The biomarker endpoints include the following:

- Biochemical markers (amylase, lipase, IL-1, IL-6, IL-8 and TNFa)
- LPL concentration, Hepatic Lipase activity and concentration, Endothelial Lipase activity and concentration
- Lipoprotein subfraction composition after ultracentrifugation: chylomicrons (CM), VLDL, IDL, LDL (low-density lipoprotein), HDL (high-density lipoprotein) and TG content.

- Apolipoprotein composition per lipid subfraction by ultra-centrifugation
- Lipoprotein concentration parameters determined by Nuclear Magnetic Resonance (NMR)

5. STATISTICAL METHODS

5.1. Demographics and Baseline Characteristics

Demographic and baseline characteristics will be summarized descriptively by treatment group and overall for the study, as well as by treatment group and overall within each cohort in the FAS population.

Continuous data will be summarized using the number of patients with data, mean, SD, median, Q1, Q3, minimum and maximum for each treatment group. Categorical and ordinal data will be summarized using the number and percentage of patients in each treatment group.

For the single-blind safety population, demographic and baseline characteristics will be summarized by all patients and by treatment group of the DBTP (i.e., evinacumab, placebo).

5.2. Medical History

Medical history will be descriptively summarized by treatment group and overall for the study, as well as by treatment group and overall within each cohort in the FAS population.

All reported patient's medical history will be presented by primary SOC and HLT. The tables will be presented by SOC sorted alphabetically and decreasing patient frequency of HLT based on the overall incidence in the study. In addition, all medical history of specific interest, primary and secondary CVD prevention including corresponding criteria, as described in Section 4.2, will be summarized by patient incidence and percentage.

The number (%) of patients will be summarized by CVD prevention status (i.e. primary and secondary CVD prevention status).

In addition, smoking status will be summarized in patients with primary CVD prevention status.

For patient disease characteristics, as described in Section 4.2, continuous data will be summarized using the number of patients with data, mean, SD, median, Q1, Q3, minimum and maximum for the study. Categorical and ordinal data will be summarized using the number and percentage of patients in the study.

5.3. Prior and Concomitant Medications

All prior medications, dictionary coded by WHO-DD, will be descriptively summarized by treatment group and overall for the study, as well as by treatment group and overall within each cohort for patients in the double-blind safety population. Summaries will present patient counts (and percentages) for all prior medications, by decreasing frequency of the overall incidence of ATC followed by therapeutic class. In case of equal frequency across anatomic or therapeutic categories, alphabetical order will be used. Patients will be counted once in each ATC category

(anatomic or therapeutic) linked to the medication but may be counted several times for the same medication.

All concomitant medications during the DBTP, dictionary coded by WHO-DD, will be descriptively summarized by treatment group, for patients in the double-blind safety population. Summaries will present patient counts (and percentages) for the concomitant medication groups described in Section 4.3 for all concomitant medications, by decreasing frequency of the evinacumab group incidence of ATC followed by therapeutic class. In case of equal frequency across anatomic or therapeutic categories, alphabetical order will be used. Patients will be counted once in each ATC category (anatomic or therapeutic) linked to the medication, hence may be counted several times for the same medication. Post-treatment medications will be summarized as described above for all medications.

For the SBTP, concomitant and post-treatment medications will be dictionary coded by WHO-DD and will be descriptively summarized as described for the DBTP. Medications will be summarized for all patients and by treatment group of the DBTP (i.e., evinacumab, placebo) for patient in the single-blind safety population. Summaries will present patient counts (and percentages).

5.4. Prohibited Medications

Listing of prohibited medications will be provided for the patients in the double-blind safety analysis set for the DBTP and SBTP.

5.5. Patient Disposition

Patient disposition includes the description of patient status at major milestone decisions in the study, as well as the patient analysis populations.

Patient study status for the DBTP will be summarized by treatment group and overall for the study, as well as by treatment group and overall within each cohort (screened patients, screen failures, and non-randomized but treated patients only). Summaries will provide the frequency (and percentage as applicable) of patients that met the criteria for the variables described in Section 4.5. Exception listings will be generated for any patient treated but not randomized, randomized but not treated, and treated differently than randomized.

DBTP patient analysis populations will be summarized by treatment group, depicting frequencies (and percentages) of patients that met the criteria for each population described in Section 3.

For the SBTP, the patient study status and patient analysis populations will be summarized by all patients and by treatment group of the DBTP (i.e., evinacumab, placebo) on the single-blind safety population for the variables described in Section 4.5

For both the DBTP and SBTP, the incidence of premature study treatment discontinuation (irrespective of the reason) and premature treatment discontinuation due to AEs will be presented graphically by treatment group in the respective safety analysis set using the Kaplan-Meier method.

5.6. Extent of Study Treatment Exposure and Compliance

The extent of study treatment exposure for the DBTP described in Section 4.6 will be assessed and summarized by treatment group, for patients in the double-blind safety analysis set. The extent of study treatment exposure for the SBTP described in Section 4.6 will be assessed and summarized for all patients and by treatment group of the DBTP (i.e., evinacumab, placebo) for patients in the single-blind safety analysis set.

5.6.1. Exposure to Investigational Product

Study treatment exposure in the DBTP and SBTP will be descriptively summarized for treatment duration and total number of infusions as described in Section 4.6. Treatment duration and total number of infusions will be summarized using the number of patients with data, mean, SD, Q1, Q3, median, minimum and maximum.

Additionally, evinacumab dosing exposure will be summarized cumulatively across the study, combining DBTP and SBTP for patients who received evinacumab in the DBTP.

5.6.2. Study Treatment Compliance

Both monitored and derived protocol deviations will be summarized for important deviations (counts of deviations), patients (incurring a deviation by count and percentage), and by type of important deviation (patient count and percentage). A patient listing of all important and minor protocol deviations will be provided.

Descriptive statistics of the infusion frequency will be summarized. A patient listing will be provided for those patients with incomplete or interrupted infusions. Cases of study treatment overdose will be reported in the AE e-CRF page and will be described in the adverse event analysis.

5.7. Analyses of Efficacy Variables

For statistics where international and conventional units do not impact the results (e.g. means and least square (LS) means for percent changes from baseline, rates of patients below a threshold), derivations will be calculated and statistical models will be run using conventional units. For other statistics (e.g. descriptive statistics at baseline and over time, absolute changes from baseline), derivations will be presented in both international and conventional units.

Statistical analyses for the primary efficacy endpoint will be conducted as described below and will be completed during the final efficacy analysis (Section 7). Only measurements collected at the protocol scheduled time point (as defined by e-CRF visit label) will be used for the analyses.

5.7.1. Analysis of Primary Efficacy Variable

The primary efficacy analysis will assess within-patient percent change in TG over 12 weeks of evinacumab treatment (double-blind period for patients randomized to evinacumab and single-blind period for patients randomized to placebo).

The point estimates of TG percent changes between the placebo period and each observation week will be calculated using a Mixed-effect Model for Repeated Measures (MMRM) method in the FAS population. A natural log transformation will be applied to the TG levels prior to

analysis, aiming to provide a relatively normal data distribution (residuals will be examined for normality prior to proceeding with the analysis). The MMRM model will assess within-patient treatment comparisons (using an unstructured covariance matrix), while accounting for baseline TG, study visit, and baseline TG by study visit interaction. Note that study visits will be adjusted to start of evinacumab in order to pool data from both randomized groups of patients for this analysis. Since the comparison of study visits yields the within-patient comparisons of study treatments (ie, week 12 [after 12 weeks of treatment with evinacumab] compared to baseline at week 0 [after 4 weeks of treatment with placebo] for patients randomized to evinacumab and week 24 [after 12 weeks of treatment with evinacumab] compared to baseline at week 12 for those randomized to placebo), contrast and estimate statements will be used to assess treatment effects (least squares [LS] means with confidence intervals) and comparisons (LS mean ratio with CI). Within-patient comparisons will include all patients. In the event the MMRM model covariance matrix does not converge or normality is not achieved with the natural log transformation, then other transformations will be explored, including ranks.

To reduce variability of TG baseline measurements, baseline at week 0 for patients randomized to active treatment is the mean of the 3 log-transformed measurements at day -28, day -14, and week 0. Baseline at week 12 for patients switching from placebo to active is the mean of 3 log-transformed measurements at weeks 6, 8, and 12. Additional exploratory analyses may be carried out using the average of all available TG observations prior to first dose of active treatment, if no trend over time in those measurements is discernable.

The estimate of the log TG mean ratio (week 12/baseline at week 0 for patients randomized to evinacumab and week 24/baseline at week 12 for those randomized to placebo) and the log of the standard deviation derived from the MMRM model (ie., LS mean ratio with CI) based on observed results from the patients without LOF mutations in genes in the LPL pathway will be reviewed for 40% reduction.

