4.7.2. Lipids Variables

Potential clinical benefits of study treatment will be explored through the following lipids parameters: LDL-C (Ultracentrifugation), HDL-C, total-C, fasting TG, non-HDL-C, Apo B, Apo A1, Apo CIII, Apo B/Apo A1 ratio, and Lp(a).

Baseline TG is defined as the mean of the last 2 measurements during the placebo run-in (day -28, day -14) and week 0.

Lipids parameters will be collected in a fasted state over the course of the study at time points listed in [Appendix 10.4](#), and sent to the central laboratory for evaluation, including scheduled and unscheduled blood draws. Both the absolute change from baseline and the percent change from baseline will be calculated for each lipids parameter, and derivations will be presented in

both international and conventional units. TG measurements with missing fasting status will be excluded from the summaries.

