5.7.1.1. Sub-group Analyses

To assess the homogeneity of the treatment effect across various subgroups, treatment-by-subgroup factor, time point-by-subgroup factor and treatment-by time point-by subgroup factor interaction terms and a subgroup factor term will be added in the primary MMRM model. Within-patient contrast and estimate statements will be used to assess treatment effects (least squares [LS means with confidence intervals) and comparisons (LS mean ratio with CI). In order to handle imbalances between subgroup factors levels, population weights will be used in the analysis model.

The following subgroups of interest will be evaluated, assuming there are enough patients in each subgroup level to perform the evaluation.

- Cohort assignment (1,2 and 3) as defined at the time of the analysis

A graph will depict the mean (+/- SE) TG concentrations over time for each genotype subgroup.

Nominal p-values for testing mean change from baseline >0 and $>40\%$ at each time point in each cohort may be computed for information purposes. Since this is an exploratory study, control of the overall type-I error is not applicable for statistical testing. Any p-values provided for outcome measures are for descriptive purposes only.

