5.7.2. Analyses of Lipids Variables

Descriptive statistical analyses for the lipids defined in Section 4.7.2 will be summarized by treatment group and overall for the study, as well as by treatment group and overall within each cohort in the FAS population.

For descriptive summaries, percent change, and/or when appropriate, absolute change from baseline in conventional (US) and international units will be provided for lipids (LDL-C, Apo B, total-C, TG, non-HDL-C, Lp(a), Apo CIII, Apo A-1, and ratio Apo B/Apo A-1) at each protocol scheduled time point (as defined by e-CRF visit label) for each treatment group. For TGs, measurements on not-fasting patients will be excluded. Observed lipid values will be used, ie, imputation of missing values is not planned. For the evinacumab treated group, within-patient testing of endpoints with a non-normal distribution will use the Wilcoxon signed-rank test and endpoints with a normal distribution will use the paired t-test to evaluate the mean differences between baseline and each protocol visit. The p-value will be provided for descriptive purposes only.

Figures will be produced to support the summary tables for percent change and/or when appropriate absolute change from baseline. The plot will contain mean percent change +/- standard error (SE) through the study visits for each lipid variable (except TG and Lp(a)) by treatment group. For TG and Lp(a), plots will contain the median percent and /or absolute change from baseline along with quartiles (Q1 and Q3) over time by treatment group.

In addition, all lipids measurements (scheduled and unscheduled) will be included in patient listing.

During the SBTP, efficacy variables will be explored through descriptive statistics at each protocol scheduled visit for the total patients administered single-blind study treatment (total), as well as by the patient subgroups of study treatment received in the double-blind treatment period (i.e., evinacumab, placebo). Descriptive statistics will include the observed values of the same parameters as described for each variable in the DBTP, for patients in the single-blind safety analysis set.

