5.11. Analysis of PRO Variables

Descriptive statistical analyses for the PRO variables defined in Section 4.11 will be summarized by treatment group and overall for the study, as well as by treatment group and overall within each cohort in the PRO population.

Only measurements collected within 14 days prior to the protocol scheduled time point (as defined by e-CRF visit label) will be assigned to that visit and used for the analyses. If more than 7 days of data are collected during this period, only 7 days of the data (closest to the visit date) will be used. PRO evaluation at the visit is considered non-missing if a patient completes the questionnaire for at least four days for this visit. Missing PRO evaluations will not be imputed.

A cross-sectional analysis will be performed for each available PRO variable for the SBTP and the DBTP. The HAP-SS and HAP-DB domains and total scores including change from baseline will be reported at each time point. The number of patients with non-missing values, mean, standard deviation, median, Q1, Q3, minimum value, and maximum value will be reported. Summaries for the DBTP will be presented by treatment groups (evinacumab, placebo). Summaries for the SBTP will be presented by all patients and by treatment group in DBTP (i.e., evinacumab, placebo).

During the DBTP the difference in change score from baseline between the treatment groups will be calculated and presented as the number of patients with non-missing values, mean, 95%

confidence interval (if data is normally distributed), standard error, median, Q1, Q3, minimum value, and maximum value at each time point. No formal inferential testing will be performed. Summaries will be descriptive in nature.

The number and percentage of stomach pain, pain, and abdominal symptom free days, and avoidance of meals, at each evaluation/visit (calculated over the seven days prior to the visit), will be presented at each time point for all patients (SBTP) and for each treatment arm (DBTP). To take account of varying numbers of completed HAP-SS and HAP-DB scores over the seven days prior to each visit (minimum number = 4, maximum number = 7), percentage scores will be calculated using both a denominator of 7 and a denominator of the number of days of available data.

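### No evinacumab/placebo TG ratio is planned, the subgroup model uses an undefined treatment factor, and the protocol's week 0 baseline sensitivity analysis is missing from the SAP

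*SAP*

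**What the plan says.** SAP 5.7.1 defines the primary analysis: "The primary efficacy analysis will assess within-patient percent change in TG over 12 weeks of evinacumab treatment". To do this, "study visits will be adjusted to start of evinacumab in order to pool data from both randomized groups of patients for this analysis". The mixed model for repeated measures (MMRM) is fitted to log TG with baseline TG, visit and their interaction, and an unstructured covariance. Baseline is the mean log TG at day -28, day -14 and week 0 for patients randomised to evinacumab, and at weeks 6, 8 and 12 for those randomised to placebo. The resulting post/pre ratio is then assessed in the patients without loss-of-function (LOF) mutations: "observed results from the patients without LOF mutations in genes in the LPL pathway will be reviewed for 40% reduction".

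Elsewhere in the SAP:

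- 5.7.2: "Descriptive statistical analyses for the lipids defined in Section 4.7.2 will be summarized by treatment group and overall for the study", and also by arm within cohort, with plots by arm. Here the baseline is common to both arms (4.7.2): "Baseline TG is defined as the mean of the last 2 measurements during the placebo run-in (day -28, day -14) and week 0". Testing is confined to one arm: "For the evinacumab treated group, within-patient testing of endpoints with a non-normal distribution will use the Wilcoxon signed-rank test".
- Appendix 10.1 answers No to supportive and to other analyses of the primary endpoint.
- 5.11, for patient-reported outcomes only: "During the DBTP the difference in change score from baseline between the treatment groups will be calculated and presented".
- 5.7.1.1, for cohort: treatment-by-subgroup, time-by-subgroup and "treatment-by time point-by subgroup factor interaction terms and a subgroup factor term will be added in the primary MMRM model".

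Protocol 10.4.3.1 commits to repeating the combined-sequence TG analysis with the week 0 baseline for everyone, and to checking the TG time course in the run-in. SAP 5.7.1 contains neither. SAP 1.2.4 item 4, which covers that protocol section, lists only the removal of the posterior probability and a rewording of the baseline mean.

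**The concern.** A post/pre ratio carries any time trend, change in diet or change in adherence that occurs alongside the drug. The placebo arm is the only 12-week record without drug, but in the primary model its double-blind TG values enter only at weeks 6, 8 and 12, averaged into a baseline. The protocol's run-in check would cover 4 weeks, against 12 weeks of treatment, and the SAP does not carry even that over. The 40% review supports development planning (SAP 1.2.4), so it matters whether the 40% is a drug effect or a drug effect plus drift.

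The subgroup model is the main genotype analysis. With treatment undefined, two programmers could fit different models to the same data. The unlisted loss of the week 0 repeat removes the one planned check on whether using different baselines in the two sequences affects the pooled result.

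**Working it through.** **Reproducing the plan's precision.** SAP 2.2 uses a log-scale SD of 0.5 and a 90% CI. With log(0.6) ± t(0.95, n-1) × 0.5/√n, back-transformed, N=10 gives 19.8-55.1% (stated 20-55%) and N=12 gives 22.2-53.7% (stated 22-54%). Both reproduce. Both are one-sample post/pre intervals; the SAP gives no between-arm TG precision.

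**What a between-arm ratio would deliver.** SE = √(0.5²/n₁ + s²/n₂), with t on n₁+n₂-2 degrees of freedom, around log 0.6. The evinacumab SD of 0.5 is from SAP 2.2. The documents give no placebo TG SD, so s is assumed at 0.25, 0.5 and 0.7. Allocation is 2:1; the sizes are the approximate maximum of 50 and cohort 3 at 27 and 15. Entries are 90% CIs for the percent reduction.

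| Evinacumab vs placebo | s = 0.25 | s = 0.5 | s = 0.7 | Post/pre, same patients |
|---|---|---|---|---|
| 33 vs 17 | 28 to 50 | 23 to 53 | 17 to 56 | 32 to 47 |
| 18 vs 9 | 23 to 53 | 15 to 58 | 6 to 62 | 29 to 49 |
| 10 vs 5 | 15 to 57 | 3 to 63 | -12 to 68 | 25 to 52 |

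Worked example at 33 vs 17, s = 0.5: SE = √(0.25/33 + 0.25/17) = 0.149, against 0.5/√50 = 0.071 post/pre, a ratio of 2.1. Across s = 0.25 to 0.7 the SE ratio runs from about 1.5 to 2.7.

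**Sensitivity to drift.** Take a pooled ratio of 0.60 and a placebo change of -d over 12 weeks. If drift affects every patient's treated period, the net reduction is 1 - 0.6/(1-d). If it affects only the immediate-start two thirds, it is 1 - 0.6/(1-d)^(2/3).

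- d = 10%: 33.3% or 35.6%
- d = 20%: 25.0% or 30.4%
- d = -10% (placebo rises): 45.5% or 43.7%

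These values of d are illustrative, not estimates of bias.

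**The subgroup terms.** I counted the independent fixed effects for 48 patients (cohorts of 9, 12 and 27, split 2:1), with visits at weeks 2, 4, 6, 8 and 12 after starting evinacumab for immediate start and 4, 8 and 12 for delayed start. The primary model has 10; adding cohort and cohort-by-visit gives 20. Adding the treatment interactions leaves 20 if treatment means drug received, because the post-baseline records are all on evinacumab apart from early-termination visits after discontinuation. It gives 29 if treatment means randomised arm, and the extra terms then compare immediate with delayed start. Neither reading is an evinacumab/placebo effect.

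**The dropped checks.** The protocol's week 0 repeat covered two quantities: the TG reduction and the posterior probability. SAP 1.2.4 explains why the second went; nothing there explains the first. SAP 5.7.1 mentions trend only as a condition for an optional analysis that averages all TG values before active treatment.

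**The case against.** The strongest reply is that a between-arm TG contrast was never planned. Protocol 3.2.1 describes a fixed-sequence study with an intrapatient primary aim and justifies the double-blind period by unbiased assessment of safety. Protocol 10.1 plans no formal testing. Where the protocol wanted between-arm contrasts, for PET and MRI, it says so in 10.4.3.2. This stands: a reader might infer that the SAP departs from the protocol on this point, or that the primary analysis is invalid, and the documents support neither.

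A reader might also infer that placebo drift would stay hidden. It would not: 5.7.2 shows TG change by arm at each scheduled visit on one run-in baseline, with medians and quartiles plotted. What is missing is a specified, baseline-adjusted ratio with an interval. Regression to the mean is a lesser worry than it may seem, since the screening TG values are in neither baseline.

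The precision objection also stands in part. The primary question concerns patients without LOF mutations, so the cohort 3 rows are the relevant ones, and the smallest is close to uninformative. The 33 vs 17 row assumes a ratio of 0.60 across all cohorts, which Protocol Section 1 makes uncertain: it reports that some patients with LPL and other mutations did not show robust lowering.

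On the subgroup model, 5.7.1.1 goes on to ask for within-patient contrasts, and under the drug-received reading the fit is unchanged. The problem is therefore one of specification; it does not follow that the cohort results would be wrong. On the third point, week 24 change from the run-in baseline may be available descriptively for placebo patients under 5.7.2, but that does not replace the pooled model repeat.

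**Conclusion.** The concern holds in a limited form, as a recommended change. The pooled within-patient estimate is a legitimate primary analysis. The missing TG contrast is a gap in a randomised placebo-controlled plan, not a protocol departure. Its size depends on placebo drift, which the documents do not give, so the drift figures show sensitivity only.

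A supportive contrast would be usable overall and weak in the target subset. With ratio 0.60 and log-SD 0.5 assumed in both arms, the 90% CI is 15-58% at 18 vs 9 and 3-63% at 10 vs 5. Cohort 3 stands in here for the patients without LOF mutations; this is an assumption, because that cohort also takes patients with no genotype information.

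The treatment interactions in 5.7.1.1 cannot be implemented unambiguously as written. The loss of the TG-reduction half of the week 0 sensitivity analysis, and of the run-in trend check, is an unlisted departure from Protocol 10.4.3.1.

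**What to change.** 1. Keep the pooled estimate primary. Add one supportive MMRM on log TG for the double-blind period with arm, visit, arm-by-visit, run-in baseline log TG (day -28, day -14 and week 0 in both arms), baseline-by-visit and cohort. Use an unstructured covariance and name a simpler fallback structure in advance. Report the week 12 evinacumab/placebo ratio with a 90% CI overall. A cohort main effect alone cannot give a ratio for patients without LOF mutations, so refit the model in that subset without the cohort term, or add arm-by-subgroup and arm-by-visit-by-subgroup terms. Label that result descriptive.
2. In SAP 5.7.1.1, replace the treatment interactions with cohort and cohort-by-visit terms, and report cohort-specific LS mean post/pre ratios.
3. Restore the pooled MMRM on the common week 0 baseline and the run-in TG trend check, and amend Appendix 10.1 to match. Listing their removal in SAP 1.2.4 would tidy the record but would not bring the checks back.

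The cost is SAP wording, one added model and one restored repeat, all on data already collected. The downsides are an interval with an SE about 1.5 to 2.7 times that of the post/pre estimate, and a risk of non-convergence in the smallest subset, which is why the fallback must be stated beforehand.
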